#### **Specific Aim 2: To determine if, and which, maternal side effects are more common at 1 hour, 4 hours, and time of delivery with an alternate magnesium sulfate dosing protocol in obese women.**

## Hypotheses

We hypothesize that a randomized trial of alternate dosing of intravenous magnesium in obese women will allow us to:

1. Determine optimal antenatal magnesium dosing protocols to optimize therapeutic serum magnesium levels in obese preeclamptic women.
2. Determine significant covariates and correlations between maternal serum magnesium levels and maternal side effects and outcomes.
3. Determine the optimal antenatal magnesium dose to minimize adverse drug effects while maintaining a therapeutic serum magnesium level in the mother.

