## Background

Magnesium sulfate is one of the most commonly prescribed intravenous medications in contemporary obstetric practice. Magnesium is the drug of choice for preventing seizures in women with preeclampsia, a leading cause of maternal morbidity and mortality. More than 77% of expectant mothers experience side effects related to antenatal magnesium administration. Magnesium may also negatively impact obstetric outcomes and lead to adverse neonatal effects. Current intravenous magnesium treatment for various indications (preeclampsia, tocolysis, neuroprotection) follows standardized protocols (4-6 g loading dose followed by an infusion at 1-2 g/h) based on institution preference. These protocols proposed by Prichard in 1979 were derived clinically to provide estimated serum magnesium levels necessary to treat eclamptic seizures. These standardized protocols are administered unaltered to all patients, without adjustment for maternal or fetal factors that may affect serum magnesium levels. The PI has previously constructed a detailed, robust pharmacokinetic (PK) model of intravenous magnesium sulfate administered antenatally to expectant mothers and exposed fetuses with the aim of optimizing maternal and fetal outcomes while preventing maternal and neonatal overdosing and morbidity associated with current magnesium treatment protocols.

The PK data derived from this pilot study at another academic institution suggests obese pregnant women may require an increased dose of magnesium sulfate to maintain a therapeutic serum level for prevention of eclamptic seizures ( $\geq 4.8$  mg/dL). In that pilot study, statistical modeling suggested more obese preeclamptic women take approximately twice as long as non-obese preeclamptic women to achieve steady state levels of the drug.

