## **2. Procedures Involved**

After obtaining informed consent, the subject will be randomly assigned to one of two treatment groups: 1.) a starting dose of magnesium sulfate of 4g, followed by 1g every hour until 24 hours after delivery (the current standard regimen used at OHSU), or 2.) a starting dose of magnesium sulfate of 6g, followed by 2g every hour until 24 hours after delivery. There will not be a placebo arm of the study; only a smaller dose or larger dose of magnesium sulfate administered. Although the study dosing is randomized, it is not blinded and both the investigator and the research subject may know what dose of magnesium sulfate is being administered. If the subject is found to be symptomatic at any point in the study, the usual clinical care will be provided, which would include checking a serum magnesium level and decreasing the dose of magnesium sulfate, if needed. Study participation will continue; however, the timing and details of the dosing change will be recorded and used for research purposes.

If there is an indwelling intravenous catheter in place for surgery, we will attempt to use it to draw blood. We will draw a sample from a vein if we are not able to collect the samples from an existing intravenous catheter.

Specimens will be collected as follows:

- Serum magnesium before the administration of magnesium sulfate
- Serum magnesium at 1 hour, 4 hours, and delivery after the initial dose of magnesium sulfate
- Each sample will be 5-10 ml (approximately 1-2 teaspoon). The total drawn for all samples will likely not exceed 5 teaspoons.
- Urine samples will be obtained if possible at these same time points.
- If the patient requires spinal anesthesia for cesarean delivery, 0.5 ml (a few drops) of spinal fluid will be taken to check for magnesium levels at the same time the spinal anesthetic is being performed.

	Visit 1 Day 1	Visit 2 Day 1	Visit 3 Day 1	Visit 4 Day 1
Consent Discussion, Screening tests and medical history	X			
Blood draw (1 teaspoon)	X	X	X	X
Urine sample (2 teaspoons)	X	X	X	X
Time (after magnesium sulfate administration)	baseline	1 hour	4 hours	Time of delivery (within 20 mins)

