**Information that may be abstracted from the subject's chart includes** maternal age, race, height, weight, renal function and creatinine clearance (if available), maternal heart rate variability, medical comorbidities, chorioamnionitis, labor duration, mode of delivery, gestational age, cord pH, and birthweight. These covariates may be considered in the pharmacokinetic model. These covariates demonstrate biological plausibility, and have physiologic potential to significantly impact the optimal dosing of magnesium. Additionally, maternal side effects (flushing, sedation, nausea, vomiting, respiratory rate, oxygen saturations, blood pressure, heart rate, and patella tendon reflex depression) will be assessed prospectively by a physician or research assistant at the same time-points as the PK sampling. Neonatal data will include NICU admission, need for respiratory support, need for blood pressure support, electrolyte abnormalities, feeding difficulties, intraventricular hemorrhage, necrotizing enterocolitis, seizures, sepsis, respiratory distress syndrome, retinopathy, patent ductus arteriosus, fetal/infant death.

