## **6. Provisions to Monitor the Data to Ensure the Safety of Subjects**

The investigators and study staff are responsible for recording the data, and they will be verifying its accuracy throughout the process. The PI will be reviewing the data in-depth periodically throughout the study. The PI will also be overseeing that the study procedures are being carried out as per the approved protocol via close supervision of the study visit and procedures and through frequent communication with the other investigators and staff. Anytime that an AE, SAE, UP or protocol deviation is reported by an investigator or study staff, the PI will review and assess the data, and proceed as per OHSU reporting policy. Otherwise, the PI entity will be reviewing the records periodically throughout the study. All adverse events will be assessed and reportable UPs will be submitted to the IRB, if judged related to the study protocol. All data will be stored for future analysis and stored in the MFM Repository eIRB#7285

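### Does the plan miss maternal harms because scheduled assessment ends at delivery while both infusions run for another 24 hours?

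*Combined protocol and SAP*

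**What the plan says.** Section 2 (Procedures Involved) defines the two regimens as "a starting dose of magnesium sulfate of 4g, followed by 1g every hour until 24 hours after delivery" and "a starting dose of magnesium sulfate of 6g, followed by 2g every hour until 24 hours after delivery". The visit table schedules serum magnesium at baseline, 1 hour, 4 hours and delivery (within 20 minutes), with nothing later. Maternal side effects "will be assessed prospectively by a physician or research assistant at the same time-points as the PK sampling".

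Specific Aim 2 asks which "maternal side effects are more common at 1 hour, 4 hours, and time of delivery". Specific Aim 1 concerns the level at 4 hours and Aim 1a the level at delivery. Study Design states the outcome at those same two time-points.

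Two provisions are not tied to the visit schedule. Under section 2, a woman who becomes symptomatic receives usual care, including a serum level, and "the timing and details of the dosing change will be recorded and used for research purposes". Under section 6, "All adverse events will be assessed and reportable UPs will be submitted to the IRB". Neither names delivery as a cut-off.

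For the infant, collection does reach past birth: "Neonatal data will include NICU admission, need for respiratory support, need for blood pressure support, electrolyte abnormalities, feeding difficulties", among other items.

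**The concern.** The randomised treatment does not stop at delivery, but scheduled maternal observation does. The final 24 hours carry the full contrast in infusion rate, 2 g/h against 1 g/h. The Background adds that, in the pilot modelling, more obese women "take approximately twice as long as non-obese preeclamptic women to achieve steady state levels of the drug", so a woman who delivers early might still have a rising level when sampling stops. Neonatal outcomes after birth are listed, while no postpartum maternal item is.

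At stake would be the safety account of the higher-dose regimen. Study Design says the findings may be used to tailor treatment. If harms clustered in the postpartum day, a comparison ending at delivery would not show them systematically by arm.

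**Working it through.** **1. Time-points asked about, against time-points collected.**

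| Question | Where stated | Time-points asked | Scheduled data |
|---|---|---|---|
| Therapeutic level | Specific Aim 1 | 4 h | serum magnesium at 4 h |
| Therapeutic level | Aim 1a | delivery | serum magnesium at delivery |
| Trial outcome | Study Design | 4 h and delivery | both |
| Side effects | Specific Aim 2 | 1 h, 4 h, delivery | all three |
| Best dosing | Hypotheses 1 and 3 | antenatal | all samples up to delivery |
| Level against side effects | Hypothesis 2 | none given | paired level and side effects at each sampling time |

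No row needs a scheduled maternal measurement after delivery. Hypothesis 2 has no time limit, but it needs paired observations, and those exist at every sampling time.

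**2. The plan's one sizing figure.** Number of Subjects gives 18 per arm. Inputs from that section are rates of 0.50 and 0.95. Two-sided 5% and 80% power are assumptions, because neither is stated.

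- n = [1.96·√(2 × 0.725 × 0.275) + 0.842·√(0.25 + 0.0475)]² / 0.45² = 14.2, or 15 rounded up.
- With continuity correction: (14.2/4)·[1 + √(1 + 4/(14.2 × 0.45))]² = 18.4, or 19 rounded up, close to the stated 18.

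This figure belongs to the 4-hour comparison. Nothing after delivery enters it.

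**3. Planned dose after the last scheduled assessment.** Alternate: 2 × 24 = 48 g. Standard: 1 × 24 = 24 g. The documents give no time from start to delivery (h hours), so a range is assumed. Totals are 6 + 2(h + 24) g and 4 + (h + 24) g.

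| h (assumed) | Alternate total; share after delivery | Standard total; share after delivery |
|---|---|---|
| 4 | 62 g; 77% | 32 g; 75% |
| 12 | 78 g; 62% | 40 g; 60% |
| 24 | 102 g; 47% | 52 g; 46% |
| 48 | 150 g; 32% | 76 g; 32% |

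The share is large but nearly equal in the two arms. It is planned grams, not serum exposure or harm.

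**4. Could levels still be rising?** The documents give no half-life. Assume one compartment, unchanged clearance after delivery, no dose reduction, and a half-life of 4 to 8 hours. With A(t) = L·e^(−kt) + (R/k)(1 − e^(−kt)) and k = ln 2 / half-life, compare A(h + 24) with A(h), using L = 6, R = 2 for the alternate arm.

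- Delivery at 4 h: 8.77 to 11.50 g (+31%) with a 4-hour half-life; 11.00 to 21.57 g (+96%) with an 8-hour half-life.
- Delivery at 12 h: +6% to +31%. At 24 h: +1% to +9%. At 48 h: 0% to +1%.
- No rise at all if the half-life is at most ln 2 × 6/2 = 2.1 h.

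The answer runs from nothing to a near doubling, depending on inputs the documents do not supply. Charting clinically ordered levels would not settle it, because those levels come from selected women at unplanned times.

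**5. What extended maternal chart abstraction could show.** With 18 per arm:

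- 0/18: two-sided 95% upper limit 1 − 0.025^(1/18) = 18.5%.
- 0 v 0: Newcombe 95% interval for the difference -18 to +18 points.
- 2 v 0: difference 11 points, interval -8 to 33.
- Chance of at least one event in an arm, 1 − (1 − p)^18: 30%, 60% and 85% for p = 2%, 5% and 10%.

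Such counts could describe events but could not separate the arms.

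**The case for a change.** The strongest opposing case is that the postpartum day is part of the regimen, that a reader weighing the higher dose will ask what happened to the mothers during it, and that data not collected uniformly are hard to recover. Adding a few chart fields for 36 inpatients would need no extra sample. The existing safety net is also loose: section 6 acts on reported events and states no window, section 2 states no end of participation, and it speaks of recording a dosing change whereas section 7a also foresees discontinuation. Section 7a names pulmonary edema as a known effect, but the side-effect list in section 2 does not include it. The visit table labels the delivery visit Day 1, which points towards short intervals, where the share of dose after delivery is largest.

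These observations are accurate. What stands is limited: the maternal adverse-event window is unstated, and no systematic comparison of maternal side effects covers the postpartum day. They do not show an error. Stopping the drug for a serious side effect would ordinarily count as an adverse event under section 6, and the abstraction list in section 2 is worded permissively, so an unnamed item is not excluded.

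The suggested addition also has weaknesses of its own. Reflexes would be assessed prospectively before delivery and taken from charts afterwards, so counts before and after would not be comparable. Pulmonary edema would be new collection in both periods. In an open-label trial, charting, dose reduction and ordering of levels may differ by arm.

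**Conclusion.** The concern does not hold. The facts behind it are right: 24 hours of randomised infusion, 48 g against 24 g planned, follow the last scheduled maternal assessment. But the stated aims and outcome end by delivery, the schedule supplies every time-point they need, and the provisions for dose changes and adverse events carry no stated stop at delivery. Followed as written, the plan answers its own question, and neither the 4-hour comparison nor the comparison under Specific Aim 2 changes.

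Studying the postpartum infusion would be a separate, optional question. At 18 per arm it could be answered only descriptively, with an interval of -18 to +18 points even when no events occur.

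This conclusion rests on reading the aims as worded and on taking the unscheduled safety provisions to apply while a woman is still receiving study drug, which the documents do not say expressly. It does not depend on the assumed half-life or time to delivery. The consequence for interpretation is modest: the scheduled maternal side-effect results describe the period up to delivery, not the whole infusion.

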### 3. Data and Specimens

#### a. Handling of Data and Specimens

Blood, urine, and rarely cerebrospinal fluid specimens will be assigned a unique identifier that will be associated with the subject's name and medical record number for initial laboratory analysis. After the magnesium level is determined, only the unique identifier will be present in the research database. The specimens are generally stored in the laboratory for approximately 5 days and then stored in the MFM repository (eIRB#7285). They will be transported to the laboratory through the pneumatic tube system at OHSU Hospital. In the event a CSF sample is

obtained, this sample would be stored in laboratory space for the Department of Obstetrics & Gynecology – WHRU freezers. The PI and research staff are responsible for transport of all specimens.

**b. Sharing of Results with Subjects**

Laboratory results that are part of the usual care and clinical decision making process will be shared with the subjects and providers, however, overall study results will take a much longer time to generate and will not be shared at the individual level. The OHSU Hospital Laboratory responsible for testing the specimens is CLIA certified.

**c. Data and Specimen Banking**

Specific data that may be banked includes maternal serum samples, urine samples, and CSF samples. While specimens will not be used for genetic research, they may be stored longer than 5 days for the purpose of correlating tissue levels of magnesium with clinical events. In the event the specimens are sent to the MFM Repository eIRB#7285, they will retain their unique identifier. Only the PI will be able to access the specimens and they will be retained for an indefinite period of time.

**4. Data Analysis**

Univariate and multivariate mixed-effects modeling will be utilized to assess the impact of various covariates on the outcome of serum magnesium level at different time points after magnesium sulfate administration. As previously described, assuming 95% of normal weight women have therapeutic serum magnesium levels after 4 hours of administration, we anticipate that 18 patients (36 total) are needed in each dosing group to detect a 50% difference in the proportion of women with a  $\text{BMI} \geq 35 \text{ kg/m}^2$  who have therapeutic magnesium levels 4 hours after magnesium sulfate administration. Based on current patient load, which includes treatment of approximately 40 preeclamptic patients per month, and the additional inclusion criteria of the disease severity requiring magnesium sulfate administration, as well as a maternal  $\text{BMI} \geq 35 \text{ kg/m}^2$ , and anticipated number of patients declining study participation, we anticipate potential enrollment of 1-2 patients per week.

**5. Privacy, Confidentiality, and Data Security**

All information collected as part of the study will be stored on an encrypted, password protected computer that will only be available to the PI and essential trained research personnel. Hard copy data collection forms will be stored in a locked cabinet in the PI's administrative office. Separation of identifiers from data and specimens will take place as soon as subjects' participation has ended and only the PI and research personnel will be able to relink the data in the future if needed.

Standard institutional practices will be followed as described in the OHSU Information Security and Research Data Resource Guide ([http://ozone.ohsu.edu/cc/sec/isg/res\\_sec.pdf](http://ozone.ohsu.edu/cc/sec/isg/res_sec.pdf)) to maintain the confidentiality and security of data collected in this study. Study staff will be trained with regard to these procedures. Paper files will be stored in locked filing cabinets in restricted access offices at OHSU. Electronic data is stored on restricted drives on the OHSU network. Access to data/specimens is restricted to study personnel. Access to data requires OHSU password authentication. Upon enrollment, subjects will be assigned a code that will be used instead of their name, medical record number or other personally identifying information. Electronic files for data analysis will contain only the subject code.

Codes will not contain any part of the 18 HIPAA identifiers (initials, DOB, MRN) The key associating the codes and the subjects personally identifying information will be restricted to the PI and study staff. The key will be kept secure on a restricted OHSU network drive in a limited access folder.

## **6. Provisions to Monitor the Data to Ensure the Safety of Subjects**

The investigators and study staff are responsible for recording the data, and they will be verifying its accuracy throughout the process. The PI will be reviewing the data in-depth periodically throughout the study. The PI will also be overseeing that the study procedures are being carried out as per the approved protocol via close supervision of the study visit and procedures and through frequent communication with the other investigators and staff. Anytime that an AE, SAE, UP or protocol deviation is reported by an investigator or study staff, the PI will review and assess the data, and proceed as per OHSU reporting policy. Otherwise, the PI entity will be reviewing the records periodically throughout the study. All adverse events will be assessed and reportable UPs will be submitted to the IRB, if judged related to the study protocol. All data will be stored for future analysis and stored in the MFM Repository eIRB#7285

## **7. Risks and Benefits**

### **a. Risks to Subjects.**

The possible risks of obtaining blood samples from a vein in the arm are pain, bruising, fainting, and rarely, infection. This risk is extremely small as sterile supplies will be used, and all hospital protocols will be followed.

Magnesium sulfate is known to have associated side effects (i.e. nausea, flushing, palpitations, headache, malaise, sweating, pulmonary edema, and loss of reflexes.) There may be some side effects we do not expect because we are still learning about different dosing of the study drug. The study drug may be discontinued or the dosing changed if subjects experience serious side effects.

One risk to taking part in this study is that the study drug or the dose administered may not be effective in helping to treat preeclampsia. This is a risk for all patients who are administered magnesium sulfate.

There are several drugs (prescription and non-prescription) that may cause problems when taken with the study drug. The investigator will carefully review all of the drugs a potential subject is taking before administering the study drug.

Possible risks of the study include a low risk of breach of confidentiality.

### **b. Potential Benefits to Subjects**

There are no benefits from participation in the study.

